**Table 1: Study Intervention Up-titration Scheme**

| Period       | Dose regimen             | Duration                      |                         |
|--------------|--------------------------|-------------------------------|-------------------------|
| First dose   | 200 µg                   | On Day 1 in the evening (pm)  | 1 tablet                |
| Up-titration | 200 µg twice daily*,\$   | From Day 2 am to Day 8 am**   | 1 tablet twice daily\$  |
|              | 400 µg twice daily*,\$   | From Day 8 pm to Day 15 am**  | 2 tablets twice daily\$ |
|              | 600 µg twice daily*,\$   | From Day 15 pm to Day 22 am** | 3 tablets twice daily\$ |
|              | 800 µg twice daily*,\$   | From Day 22 pm to Week 4 am** | 4 tablets twice daily\$ |
|              | 1,000 µg twice daily*,\$ | From Week 4 pm to Week 5 am** | 5 tablets twice daily\$ |
|              | 1,200 µg twice daily*,\$ | From Week 5 pm to Week 6 am** | 6 tablets twice daily\$ |

| Period      | Dose regimen                             | Duration                       |                          |
|-------------|--|--------------------------------|--------------------------|
|             | 1,400 µg twice daily*,§                  | From Week 6 pm to Week 7 am**  | 7 tablets twice daily§   |
|             | 1,600 µg twice daily*,§:                 | From Week 7 pm to Week 12 am** | 8 tablets twice daily§   |
| Maintenance | iMTD:
200 µg to 1,600 µg twice daily§ | From Week 12 onwards           | 1–8 tablets twice daily§ |

am morning;; iMTD individual maximum tolerated dose; pm evening.

\* Or the iMTD until Week 12.

\*\* If the dose regimen is not well tolerated or symptoms cannot be fully managed with symptomatic treatment, the duration of the titration step can be prolonged to 2 weeks.

§ For participants with moderate hepatic impairment (Child Pugh Class B) or who are concomitantly taking (a) moderate CYP2C8 inhibitor(s) the dosing frequency is once daily. These participants must take the study intervention in the morning; hence the first dose of study intervention should be taken in the morning of Day 2.

## 6.2. Preparation/Handling/Storage/Accountability

### Preparation/Handling/Storage

Study intervention supplies must be kept in an appropriate, secure area and stored according to the conditions specified on the label. Refer to the pharmacy manual/study site investigational product and procedures manual for additional guidance on study intervention preparation, handling, and storage.

### Accountability

The investigator is responsible for ensuring that all study intervention received at the site is inventoried and accounted for throughout the study. The dispensing of study intervention (number of dispensed bottles and date dispensed/number of tablets dispensed) to the participant, and the return of study intervention (date returned/number of tablets returned) from the participant (if applicable), must be documented on the intervention accountability form. Participants must be instructed to return all original containers, whether empty or containing study intervention. All study intervention will be stored and disposed of according to the sponsor's instructions. Study site personnel must not combine contents of the study intervention containers. If the participant forgets to bring the remaining study intervention to a study visit, he/she must be instructed to not take any tablets from the remaining study intervention bottle and to return it at the next visit.

Study intervention must be handled in strict accordance with the protocol and the container label, and must be stored at the study site in a limited-access area or in a locked cabinet under appropriate environmental conditions. Unused study intervention, and study intervention returned by the participant, must be available for verification by the sponsor's study site monitor during on-site monitoring visits. The return to the sponsor of unused study intervention, or used returned study intervention for destruction, will be documented on the intervention return form. When the study site is an authorized destruction unit and study intervention supplies are destroyed on-site, this must also be documented on the intervention return form.

Potentially hazardous materials such as, but not limited to, used ampules, needles, syringes and vials containing hazardous liquids, should be disposed of immediately in a safe manner and therefore will not be retained for intervention accountability purposes.

Study intervention should be dispensed under the supervision of the investigator or a qualified member of the study site personnel, or by a hospital/clinic pharmacist. Study intervention will be supplied only to participants participating in the study. The participants will receive sufficient study intervention to cover the period up to the next scheduled visit. Returned study intervention must not be dispensed again, even to the same participant. Study intervention may not be relabeled or reassigned for use by other participants. The investigator agrees neither to dispense the study intervention from, nor store it at, any site other than the study sites agreed upon with the sponsor.

### 6.3. Measures to Minimize Bias: Randomization and Blinding

#### Intervention Allocation

##### *Procedures for Randomization and Stratification*

Central randomization will be implemented in this study. Participants will be randomly assigned to 1 of 2 intervention groups based on a computer-generated randomization schedule prepared before the study by or under the supervision of the sponsor. The randomization will be balanced by using randomly permuted blocks and will be stratified by PH-specific therapy at baseline (yes vs no). The Interactive Web Response System (IWRS) will assign a unique intervention code, which will dictate the intervention assignment and matching study intervention kit for the participant. The requestor must use his or her own user identification and personal identification number when contacting the IWRS, and will then give the relevant participant details to uniquely identify the participant.

#### Blinding

This study will be performed in a DB fashion.

The investigator will not be provided with randomization codes. The codes will be maintained within the IWRS, which has the functionality to allow the investigator to break the blind for an individual participant.

Data that may potentially unblind the intervention assignment will be handled with special care to ensure that the integrity of the blind is maintained and the potential for bias is minimized. This can include making special provisions, such as segregating the data in question from view by the investigators, clinical study team, or others as appropriate until after the time of the database lock (see Section 9.3) and unblinding.

Under normal circumstances, the investigator and study personnel, the participants, sponsor personnel directly involved in the conduct of the trial, and CRO personnel involved in the conduct of the study will remain blinded to the study intervention until after completion of the first analysis timepoint (see Section 9.3), or until the study is stopped prematurely. In order to preserve the blind of each individual participant until the primary analysis (see Section 4.1), the randomization codes and, if required, the translation of randomization codes into intervention and control groups will be disclosed to those authorized and only for those participants included in the analyses for the

sponsor DMC. A statistical support group (SSG) independent from the study team will conduct the analyses and present unblinded results to the sponsor DMC (see Section 9).

The investigator may in an emergency determine the identity of the intervention by contacting the IWRS. While the responsibility to break the intervention code in emergency situations resides solely with the investigator, it is recommended that the investigator contact the sponsor or its designee, if possible, to discuss the particular situation before breaking the blind. Telephone contact with the sponsor or its designee will be available 24 hours per day, 7 days per week. In the event the blind is broken, the sponsor must be informed as soon as possible. The date, time, and reason for the unblinding must be documented in the Investigator Site file and in the appropriate section of the eCRF, and in the source document. The documentation received from the IWRS indicating the code break must be retained with the participant's source documents in a secure manner.

If a suspected unexpected serious adverse reaction (SUSAR) occurs for a participant in the study, unblinded SUSAR information will be provided to respective health authorities and Independent Ethics Committees (IECs) or Institutional Review Boards (IRBs) only. SUSARs will be reported to investigators in a blinded fashion. The intervention assignment will not be communicated to site personnel or to sponsor study team (see Section 8.4.3).

Participants who have had their intervention assignment unblinded may stay on study intervention after unblinding provided the following conditions are met: emergency unblinding for accidental or intentional overdose or medication error.

#### **6.4. Study Intervention Compliance**

Study intervention compliance is based on study intervention accountability (see Section 6.2). Study intervention compliance will be calculated by site personnel at each visit using the below formula and documented in the source data:

Compliance  $[(\text{number of tablets dispensed} - \text{number of tablets returned}) / \text{total number of tablets that should have been taken during the period}] \times 100$ .

Between visits and overall study compliance are expected to be between 80% and 120%. During the course of the study, the investigator or designated study site-personnel will be responsible for providing additional instruction to reeducate any participant who is not compliant with taking the study intervention.

#### **6.5. Concomitant Therapy**

Prestudy therapies administered up to 30 days before first dose of study intervention and any previous therapies for the treatment of PH (ERA, PDE5i, riociguat) and sarcoidosis (eg, infliximab, methotrexate, azathioprine, hydroxychloroquine, leflunomide, steroids) administered up to 90 days before the baseline RHC and 90 days before randomization, respectively, must be recorded in the eCRF at time of Screening.

Concomitant medications, except those listed below, are allowed during this study. Concomitant therapies must be recorded in the eCRF throughout the study from signing of the ICF onwards until the EOS visit (see Section 4.4.1) or date of last contact (see Section 7.3).

All therapies (oxygen supplementation, prescription or over-the-counter medications, including vaccines, vitamins, herbal supplements; non-pharmacologic therapies such as electrical stimulation, acupuncture, special diets, exercise regimens) different from the study intervention must be recorded in the eCRF. Recorded information will include a description of the generic name, start/end dates of administration (as well as whether it was ongoing at start of intervention and/or EOS), route, dose, frequency and indication.

For any concomitant therapy given as a treatment for a new condition or a worsening of an existing condition, the condition must be documented in the AE section of the eCRF.

Modification of an effective pre-existing therapy should not be made for the explicit purpose of entering a participant into the study.

The following medications and/or therapies are not allowed to be administered concomitantly with study intervention:

- Prostacyclin (epoprostenol), prostacyclin analogues (eg, treprostinil, iloprost, beraprost) or prostacyclin receptor agonists (ie, selexipag/UPTRAVI®) until study intervention discontinuation and if possible up to the post-baseline RHC at premature EOT before Week 26 (see Section 8.2.1.1.2).
- Strong inhibitors of CYP2C8 (eg, gemfibrozil) until study intervention discontinuation.
- Change in dose or initiation of new diuretics and/or calcium channel blockers within 1 week prior to RHC at Week 26.
- Any other investigational drug up to 30 days after study intervention discontinuation.

The sponsor must be notified in advance (or as soon as possible thereafter) of any instances in which prohibited therapies are administered.

Medications and/or therapies allowed to be administered concomitantly with study intervention, include, but are not limited to:

- Stable doses of PH-specific monotherapies (ie, riociguat, PDE5i, or ERA). Change in dose or initiation of new therapies for the treatment of PH are allowed as of Week 39 (Visit 6).
- Short-acting-beta-agonists (eg, salbutamol) and long-acting-beta-agonists, but must not be taken within 6 hours and 24 hours prior to spirometry testing, respectively.
- Single administration of prostacyclin or analogues used for acute vasodilator testing during an RHC procedure.
- Moderate inhibitors of CYP2C8. Dosing frequency of study intervention must be reduced to once daily if a moderate inhibitor of CYP2C8 (eg, clopidogrel, deferasirox, teriflunomide,

leflunomide) is concomitantly administered. Dosing frequency of selexipag should be reverted to twice daily when co-administration of moderate CYP2C8 inhibitor is stopped.

- Sarcoidosis-specific treatment, eg, infliximab, methotrexate, azathioprine, hydroxychloroquine, leflunomide, steroids. Initiation of new treatment or change in dose is allowed as of Week 39 (Visit 6).
- Strong inhibitors of UGT1A3 and UGT2B7 (eg, valproic acid, probenecid, and fluconazole). The effect of strong inhibitors of UGT1A3 and UGT2B7 on the exposure to selexipag and its active metabolite has not been studied. Caution is required when administering these medicinal products concomitantly with selexipag. A potential pharmacokinetic interaction with strong inhibitors of UGT1A3 and UGT2B7 cannot be excluded.

## 6.6. Dose Modification

Any dose/dosage adjustment should be overseen by medically qualified study site personnel (principal or sub-investigator unless an immediate safety risk appears to be present).

For participants who are unable to tolerate the protocol-specified dosing scheme, dose adjustments must follow the down-titration instructions (see Section 6.1).

## 6.7. Intervention After the End of the Study

After the participant has completed or discontinued the study, the investigator/delegate will explain to the participant what treatment(s)/medical care is necessary and available according to local regulations. If considered by the investigator to be in the best interests of the participant, the investigator can ask the sponsor to provide participants who completed the study and did not prematurely discontinue study intervention with selexipag. In this case, selexipag can be provided until access to commercial selexipag is possible in this indication in the participant's country of residence (according to local regulatory requirements), until selexipag can be accessed through another source in the country where he/she is living, or until the sponsor terminates clinical development of selexipag in this indication.

Investigators may re-contact the participant to obtain long-term follow-up information regarding the participant's safety or survival status as noted in the ICF (refer to Informed Consent in Section 10.3).

## 6.8. Treatment of Overdose

Overdose is defined by the intake of any single dose greater than 1,600 µg or a total daily dose greater than 3,200 µg (only in case subjects are on a twice daily regimen) ([IB selexipag](#)). For participants with moderate hepatic impairment or who are concomitantly taking moderate CYP2C8 inhibitor(s) the dosing frequency is once daily and overdose is defined by the intake of a dose >1,600 µg or a total daily dose >1,600 µg.

Isolated cases of overdose up to 3,200 µg have been previously reported. Mild, transient nausea was the only reported consequence.

In the event of an overdose, the investigator or treating physician should:

- Contact the Medical Monitor immediately.
- Evaluate the participant to determine, in consultation with the Medical Monitor, whether study intervention should be interrupted or whether the dose should be reduced.
- Closely monitor the participant for AE/SAE and laboratory abnormalities until selexipag can no longer be detected systemically (at least 3 days).
- Document the quantity of the excess dose as well as the duration of the overdosing in the eCRF.
- Institute supportive therapy as clinically indicated. Dialysis is unlikely to be effective because selexipag and its active metabolite are highly protein bound.

For more information see Section 10.4.

## 7. DISCONTINUATION OF STUDY INTERVENTION AND PARTICIPANT DISCONTINUATION/WITHDRAWAL

### 7.1. Discontinuation of Study Intervention

The decision to prematurely discontinue study intervention may be made by the participant, the investigator or sponsor personnel. A participant has the right to prematurely discontinue study intervention at any time, without any justification, by withdrawal from study intervention only or by withdrawal from any further participation in the study. The investigator must discontinue study intervention for a given participant if, on balance, he/she believes that continued administration would be contrary to the best interests of the participant.

A participant's study intervention must be discontinued if:

- The investigator considers that for safety reasons or tolerability reasons (eg, AE) it is in the best interests of the participant to discontinue study intervention.
- The participant becomes pregnant. Refer to Section 10.5, Contraceptive Guidance and Collection of Pregnancy Information.
- If hepatic impairment is suspected, a clinical assessment of severity (eg, Child-Pugh score) must be performed and fully documented. If a subject has developed severe hepatic impairment (Child-Pugh Class C) at any time during the study, the study intervention must be permanently discontinued (see Section 10.13).
- Pulmonary edema due to PVOD occurs. Should signs of pulmonary edema occur, the possibility of associated PVOD should be considered. If confirmed, the study intervention must be discontinued.
- Study intervention interruptions exceeding 14 consecutive days.
- The participant withdraws consent to receive study intervention.

If a participant discontinues study intervention prematurely before the EOMOP visit, he/she will continue to perform the visits and assessments as scheduled until the EOMOP visit, provided the participant's consent for this limited participation in the study has not been withdrawn (see Section 7.2). The participant will be asked to return for the premature EOT visit within 7 days of

last intake of study intervention and for a safety follow-up TC 30 (+5) days after the last intake of study intervention. If the premature EOT visit falls within the visit window of any other scheduled visit, these visits can be combined, and assessments will not be repeated.

If a participant discontinues study intervention prematurely before the EOMOP visit and does not agree to continue to perform the visits and assessments as scheduled until the EOMOP visit, he/she will be asked to return for the premature EOT visit within 7 days of last intake of study intervention and for a safety follow-up TC 30 (+5) days after the last intake of study intervention, provided the participant's consent for this limited participation in the study has not been withdrawn. Long-term survival follow-up information will be collected yearly until death or the time of EOMOP (see Section 7.2 and Section 8.2.2.2).

If a participant discontinues study intervention prematurely after EOMOP but before the study results are available and the treatment assignment is unblinded, he/she will be asked to return for the premature EOT visit within 7 days of last intake of study intervention and for a safety follow-up TC 30 (+5) days after the last intake of study intervention, provided the participant's consent for this limited participation in the study has not been withdrawn.

If the reason for withdrawal from the study is withdrawal of consent, then no additional assessments are allowed.

### 7.1.1. Temporary Discontinuation

Study intervention may be temporarily interrupted in response to an AE, a diagnostic or therapeutic procedure, a laboratory abnormality, or for administrative reasons.

Interruptions of study intervention must be kept as short as possible. Any study intervention interruption of 3 days or more will require a new up-titration starting with 1 tablet of study intervention (200 µg) twice daily/once daily. For each participant, the up-titration frequency will be up to the medical judgment of the investigator and based on his/her clinical evaluation of the participants' tolerability of the study drug prior to its interruption (see Section 6.1.2). Re-uptitration to a previously reached dose can be done at scheduled or unscheduled TCs or visits, respectively.

Study intervention interruptions exceeding 14 consecutive days must lead to permanent discontinuation of study intervention (see Section 7.1).

Interruptions of 1 day or more must be recorded in the eCRF.

## 7.2. Participant Discontinuation/Withdrawal from the Study

A participant will not be automatically withdrawn from the study if they have to discontinue study intervention before EOT (see Section 7.1).

A participant will be withdrawn from the study for any of the following reasons:

- Lost to follow-up.
- Withdrawal of consent.

- Death.
- Participant is poorly compliant with study procedures, visits, and assessments, preferably after evaluation and discussion between the investigator and the sponsor.
- The investigator considers that continued participation in the study would be contrary to the best interests of the participant.
- Sponsor's decision for any reason, including, but not limited to premature termination or suspension of the study.

If a participant discontinues study intervention and withdraws from the study before completing the study (see Section 4.4.2) for any reason (except for death or withdrawal of consent), every attempt should be made to schedule a last appointment/TC to assess the safety and well-being of the participant, collect unused study intervention and discuss follow-up medical care. If the reason for withdrawal from the study is withdrawal of consent, then no additional assessments are allowed. The investigator must provide follow-up medical care for all participants who are prematurely withdrawn from the study, or must refer them for appropriate ongoing care, as described in Section 6.7.

A participant who prematurely discontinues study intervention before the EOMOP visit and declines to return for scheduled visits does not necessarily constitute withdrawal of consent. Alternate follow-up mechanisms that the participant agreed to when signing the consent form apply (eg, continuing with survival follow-up, consulting with family members, contacting the participant's other physicians, medical records, database searches, and use of locator agencies at study completion), as local regulations permit.

Refer to Section 7.3 for more information on the required procedure to follow if a participant is lost to follow-up.

When a participant withdraws before completing the study, the reason for withdrawal is to be documented in the eCRF and in the source document.

Study intervention assigned to the withdrawn participant may not be assigned to another participant.

If participants prematurely discontinue study intervention or withdraw consent, participants will not be replaced.

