### Rationale for the Duration of the Study

Participants will receive DB selexipag or placebo until EOT. PVR and other hemodynamic endpoints will be assessed by RHC at Week 26, which is considered sufficient to observe hemodynamic changes. Other clinical endpoints, eg, exercise capacity and PROs will be assessed up to Week 39, and TTCW and rate of hospitalization related to PH-worsening or death will be assessed up to EOMOP.

The total duration of the study of approximately 3.5 years with variable follow-up time for individual participants is expected to allow for an evaluation of the TTCW endpoint and the long-term safety and tolerability endpoints in a blinded fashion.

In order to be able to estimate the effect of treatment initially assigned at baseline, regardless of adherence to the planned course of treatment (intent-to-treat principle), participants who prematurely discontinue the study intervention will be followed up until EOMOP.

Continued treatment with blinded study intervention for approximately 5 months beyond the EOMOP visit until the study results are available will allow investigators to make an informed decision on post-study therapy based on the primary analysis results and the actual intervention received by the study participants.

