## **8.2.2. Exploratory Endpoint Assessments**

### **8.2.2.1. Clinical Worsening and Hospitalization Related to PH-worsening**

The following data (obtained as part of other assessments) are required to derive TTCW (see Section 3): reporting of death, hospitalization, WHO FC, concomitant medications, AEs and SAEs. The following cases will be adjudicated by the CEC: hospitalization, increase (ie, worsening) in WHO FC and initiation of new PH-therapies. For all participants, assessment and reporting of any further disease progression will continue up to the EOMOP visit (see Section 4.1).

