### **9.5.1.3. Other Efficacy Analyses**

For continuous and categorical endpoints, where applicable, the response profiles over time (eg, change from baseline, proportions of participants by categorical endpoint categories) will be inspected graphically and by the usual summary statistics at each visit (with 95% CIs) up to the EOMOP visit by randomized treatment group on the RS. Two sets of profiles will be provided: one considering assessments measured on study intervention up to the EOMOP visit, and one including all data collected up to the EOMOP visit regardless of treatment discontinuations.

Time-to-event endpoints will be analyzed using the Kaplan-Meier method by randomized treatment group up to EOMOP, regardless of study intervention discontinuations.

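### Section 7.2 makes study withdrawal mandatory for undefined poor compliance, which conflicts with following all participants for disease progression to EOMOP

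*Protocol*

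**What the plan says.** Protocol Section 7.2 opens by saying that stopping study treatment does not by itself take a participant out of the study. It then gives a list introduced by "A participant will be withdrawn from the study for any of the following reasons". Beside loss to follow-up, withdrawal of consent, death, investigator judgement and sponsor decision stands this entry: "Participant is poorly compliant with study procedures, visits, and assessments, preferably after evaluation and discussion between the investigator and the sponsor".

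Other parts of the protocol commit to longer follow-up:

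- Section 8.2.2.1, on clinical worsening: "For all participants, assessment and reporting of any further disease progression will continue up to the EOMOP visit".
- Section 4.2, on the duration of the study, under an intent-to-treat aim: "participants who prematurely discontinue the study intervention will be followed up until EOMOP".
- Section 7.1, on a participant who stops treatment before EOMOP, subject to consent: "he/she will continue to perform the visits and assessments as scheduled until the EOMOP visit".
- Section 9.5.1.3: "Time-to-event endpoints will be analyzed using the Kaplan-Meier method by randomized treatment group up to EOMOP, regardless of study intervention discontinuations".
- Section 7.2 itself, on a participant who stops treatment before EOMOP and "declines to return for scheduled visits does not necessarily constitute withdrawal of consent". Other routes of contact then apply, such as survival follow-up, other physicians and medical records.

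Section 4.4.3 collects final survival status for people who left the study early, unless they withdrew consent.

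**The concern.** Poor compliance with visits arises after randomization. A rule that ends follow-up because of it lets site behaviour and patient condition decide whose later outcomes are seen. With no threshold, and with sponsor discussion optional, sites can apply the rule differently.

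The protocol itself makes loss related to outcome or arm plausible. Dose is titrated to individual tolerability (Section 6.1.3), and prostacyclin-type adverse events are expected, mostly during titration (Section 2.3.4). People who miss visits because they feel ill or tolerate treatment badly may be unevenly divided between the arms. Kaplan-Meier estimates and visit-wise summaries assume that those lost resemble those who remain, and that assumption would then be doubtful.

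**Working it through.** The main check is a comparison of texts. The plan states no figure for this point.

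**1. Is the rule mandatory?** Yes. The list is governed by *will be*, and the only qualifier on the poor-compliance entry concerns prior discussion. SAP Appendix 4 points the same way: one of its major-deviation categories covers participants who met withdrawal criteria but were not withdrawn. A site that kept a poor attender in follow-up could therefore be counted as deviating.

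**2. Which text does it contradict?**

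- Section 8.2.2.1 is the direct conflict. It covers all participants and runs to EOMOP.
- Sections 4.2 and 7.1 conflict in purpose rather than in letter. They concern people who stop treatment, and the adherence that Section 4.2 has in mind is adherence to treatment, not to visits.
- Section 7.2 is uneven within itself. Someone who stops treatment and openly declines visits can stay under alternate follow-up, whereas someone who merely attends badly must be withdrawn.

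**3. What is kept and what is lost?**

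- *Kept:* everything recorded before withdrawal; an attempted last appointment or call (Section 7.2, for those who stop treatment and withdraw); and final survival status (Section 4.4.3).
- *Lost:* later hospitalizations, WHO FC, 6MWD and adverse events, and the Week 26 PVR if withdrawal comes before that catheterization.
- *Imputation:* under protocol Section 9.5.1.1, a survivor with missing PVR gets the 75th percentile of all participants if clinical worsening was recorded, and otherwise the median of the own arm. A person withdrawn before worsening is recorded would get the more favourable kind of value.

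**4. How large could it be?** No document gives the frequency of such withdrawals, so everything after the first line below is an assumption.

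- *Plan's own figure:* GM ratio 0.70, CV 0.50, two-sided 0.05, 37 per arm (Sections 9.4 and 9.4.1). The log-scale SD is √ln(1 + 0.5²) = 0.472 and the difference is |ln 0.70| = 0.357. The normal approximation gives 37 per arm, 74 in total, with power 90.1%. This reproduces the plan.
- *Equal loss of Week 26 PVR in both arms, values not recovered:* with 5%, 10%, 15% or 20% lost, power is 88.6%, 86.9%, 84.9% or 82.8%.
- *Loss in the selexipag arm only:* suppose a fraction w is lost whose mean log PVR ratio is k SD worse than the rest of the arm. The observed arm mean is then too low by w × k × 0.472, and a true GM ratio of 1.00 appears as exp(−w × k × 0.472).

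| w | k = 0.5 | k = 1.0 |
|---|---|---|
| 5% | 0.988 | 0.977 |
| 10% | 0.977 | 0.954 |
| 20% | 0.954 | 0.910 |

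- *An event endpoint, crude:* suppose 10% against 3% are withdrawn, with event risk 30% in those withdrawn and 15% in the others. The true risks are 0.90 × 15% + 0.10 × 30% = 16.5% and 0.97 × 15% + 0.03 × 30% = 15.45%, against 15% and 15% seen. The hidden difference is 1.05 points, or 0.0105 × 37 ≈ 0.4 of one participant. This overstates the loss, because Kaplan-Meier counts events before withdrawal and deaths are still ascertained.

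**The case against.** The strongest reply has four parts.

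- *Sections 4.2 and 7.1 are about treatment, not visits.* This is correct. A reader might infer a general rule that everyone is followed regardless of any kind of adherence, but those two sections do not state one. The conflict rests on Section 8.2.2.1 and on the unevenness within Section 7.2.
- *Little is lost.* A reader might infer that outcome data are removed, or that a withdrawn participant contributes only vital status. The documents do not support that: nothing already collected is deleted, and a final safety contact is attempted. What remains true is that later non-fatal outcomes stop being collected.
- *No ready-made reduced follow-up exists for adverse events and hospitalizations.* This is largely right. For those who decline visits, continuing follow-up is yearly survival contact (Section 8.2.2.2), and the alternate contacts in Section 7.2 do not name those events. However, the off-treatment schedule (Section 1.3.2) already has six-monthly calls from Week 52 that collect AEs/SAEs and concomitant therapy, so an existing channel can be used.
- *It no longer matters.* The primary PVR estimand is while-on-treatment, all other efficacy endpoints are exploratory, and the study was stopped for slow enrollment. SAP version 3 tests no hypothesis, imputes no PVR, only lists efficacy (SAP Sections 2, 5.3 and 5.5) and reports no time to clinical worsening. This limits the consequence for the report but does not remove the contradiction in the protocol.

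**Conclusion.** The contradiction is real. Section 7.2 requires withdrawal for an undefined behaviour after randomization, while Section 8.2.2.1 requires disease progression to be followed in all participants to EOMOP. The main exposure is in the endpoints followed to EOMOP. The Week 26 PVR is exposed only if withdrawal comes before the catheterization.

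The size is unknown. The figures above show what assumed losses would do and are not estimates for this trial. That missed visits track tolerability or illness differently by arm is plausible from the design, but it is not documented. A reader might infer that the reported comparison is biased; the documents do not support that, since no efficacy comparison is tested and the number of such withdrawals is not given. The flaw lies mainly in the protocol as designed, and its effect on the final report is small.

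**What to change.** Reconcile Sections 7.2, 4.2 and 8.2.2.1:

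- Remove poor compliance from the study-withdrawal reasons in Section 7.2 and leave the other reasons as they are.
- Record missed visits and assessments as protocol deviations.
- State that, unless consent is withdrawn, such participants stay in whatever scheduled visits and six-monthly calls they will attend, with the alternate contacts of Section 7.2 and vital status up to EOMOP.

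No new SAP table is needed. SAP Section 5.2 already summarizes reasons for study termination by group, and Section 7.2 requires the reason in the eCRF. Poor compliance should be kept there as its own category, so that any withdrawals already made for it can be seen by arm.

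The cost is a short rewording, plus more incomplete records and more calls. The change does not alter the sample size of 74. It also has limits: walk tests, functional class and catheterizations that are missed stay missing, and because the six-monthly calls start at Week 52, events before then depend on the visits attended and the alternate contacts.
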